## 7.2. Method of treatment assignment

### 7.2.1. Subject identification

Subject identification numbers will be assigned sequentially to the subjects who have consented to participate in the study, according to the range of subject identification numbers allocated to each study centre. The subject identification number will be the same in the study extension. No new subjects will be recruited.

#### 7.2.1.1. Randomisation of supplies

The randomisation of supplies within blocks will be performed at GSK, using MATerial Excellence (MatEx), a program developed for use in Statistical Analysis System (SAS) (Cary, NC, USA) by GSK. Entire blocks will be shipped to the study centres/warehouse.

#### 7.2.1.2. Treatment allocation to the subject

**The treatment numbers will be allocated by component** (2 treatment numbers will be allocated for each subject – one for each vaccine/product administered).

For the second vaccination, 1 treatment number will be allocated for each subject.

#### 7.2.1.2.1. Study group and treatment number allocation

The target will be to enrol approximately 500 eligible subjects (250 in the US and 250 ex-US). Of these, 250 subjects will be randomized to 5 study groups in a 1:1:1:1:1 ratio using SBIR in the US, and the other approximately 250 will also be randomized to 5 study groups in a 1:1:1:1:1 ratio using SBIR ex-US.

Allocation of the subject to a study group at the investigator site will be performed using a randomisation system on internet (SBIR). The randomisation algorithm will use a minimisation procedure by treating study formulation (US and ex-US) as a stratification factor, and age at the time of vaccination (18-32 or 33-45 years of age) and center as minimization factors.

When SBIR is not available, please refer to the SBIR user guide or the Study Procedures Manual (SPM) for specific instructions.

After obtaining the signed or witnessed/thumb printed and dated ICF from the subject and having checked the eligibility of the subject, the study staff in charge of the vaccine administration will access SBIR. Upon providing the formulation (US or ex-US), age, centre and the subject identification number, the randomisation system will determine the study group and will provide the treatment number to be used for each dose.

The number of each administered treatment must be recorded in the eCRF on the Vaccine Administration screen.

Note that as soon as the target number of approximately 250 subjects in the US or 250 subjects ex-US has been reached, the enrolment will be frozen for this formulation.

**CONFIDENTIAL**209141 (RSV MAT-011)  
Protocol Amendment 6 Final

Since the second dose vaccination is open study, the treatment number will be allocated for each subject sequentially at each centre.

### **7.3. Blinding and unblinding**

Data will be collected in an observer-blind manner during the primary study. By observer-blind, it is meant that during the course of the study, the vaccine(s) recipient and those responsible for the evaluation of any study endpoint (e.g. safety, reactogenicity) will all be unaware of which vaccines were administered. To do so, vaccine preparation and administration will be done by authorised medical personnel who will not participate in any of the study clinical evaluation assays.

Investigators will remain blinded to each subject's assigned study treatment until completion of the primary vaccination day 181 database freeze for analysis. In order to maintain this blind, a nurse or pharmacist who will not participate in any other study related activity will be responsible for the reconstitution and dispensation of all study treatment.

After the Day 181 phone contact (C1) for a given subject, the investigator will be informed of the subject's treatment assignment and will communicate this to the subject. The study extension will then be conducted as an open label study.

Unblinded monitors and in the event of a Quality Assurance audit, the auditor(s) will be allowed access to un-blinded study treatment records at the site(s) to verify that randomisation/dispensing has been done accurately. Please refer to the SPM for details on blinding of the vaccine.

#### **7.3.1. Emergency unblinding**

Unblinding of a subject's individual treatment code should occur only in the case of a medical emergency when knowledge of the treatment is essential for the clinical management or welfare of the subject.

The emergency unblinding process consists of the automated Internet-based system (SBIR) that allows the investigator to have unrestricted, immediate and direct access to the subject's individual study treatment.

As back up process, the investigator has the option of contacting a GSK Helpdesk (refer to [Table 9](#)) if he/she needs support to perform the unblinding (i.e. he/she cannot access the automated Internet-based system).

Non-investigator physician (e.g. physician from emergency room) or subject/care giver/family member can also request emergency unblinding either via the investigator (preferred option) or via the GSK Helpdesk (back up process). Contact details of investigator and GSK Helpdesk are reported in the patient/subject card.

**CONFIDENTIAL**209141 (RSV MAT-011)  
Protocol Amendment 6 Final**Table 9 Contact information for emergency unblinding**

GSK Helpdesk
24/24 hour and 7/7 day availability
The Helpdesk is available by phone, fax and email
[contact]
For Canada, US and Puerto Rico
Toll-free number: [contact]
[contact]
email: [contact]

GSK policy (which incorporates ICH E2A guidance, EU Clinical Trial Directive and US Federal Regulations) is to unblind the report of any SAE which is unexpected and attributable/suspected to be attributable to the study vaccine(s), prior to regulatory reporting. Vaccines Clinical Safety and Pharmacovigilance (VCSP) is responsible for unblinding the treatment assignment in accordance with the specified timeframes for expedited reporting of SAEs (refer to Section 12.5.8).

A subject should continue in the study if that subject's treatment assignment is unblinded.

GSK Vaccines Clinical Safety and Pharmacovigilance (VCSP) staff may unblind the treatment assignment for any subject in case of Suspected Unexpected Serious Adverse Reaction (SUSAR) as well as in case of fatal or life-threatening cases. If the SAE requires that an expedited regulatory report be sent to 1 or more regulatory agencies, a copy of the report, identifying the subject's treatment assignment, may be sent to investigators in accordance with local regulations and/or GSK policy.

**CONFIDENTIAL**209141 (RSV MAT-011)  
Protocol Amendment 6 Final**7.4. Handling, storage and replacement of study vaccine(s)/product(s)****7.4.1. Storage and handling of study vaccine(s)**

The study vaccine(s) must be stored at the respective label storage temperature conditions in a safe and locked place. Access to the storage space should be limited to authorised study personnel. The storage conditions will be assessed during pre-study activities under the responsibility of the sponsor study contact. The storage temperature should be continuously monitored with calibrated (if not validated) temperature monitoring device(s) and recorded. Refer to the Module on Clinical Trial Supplies in the SPM for more details on storage of the study vaccine(s).

A temperature excursion is any temperature that is not in range of the label storage temperature conditions. Temperatures outside the range of label storage temperature conditions must be reported and/or documented. Temperature excursion impacting study vaccine(s) must be reported and/or documented.

In the frame of the reporting, the lack/absence of temperature monitoring documentation from a device meeting GSK requirements has to be considered as a temperature excursion.

Study vaccine(s) that are impacted by a temperature excursion may not be used and must be quarantined at label storage conditions until usage approval has been obtained from/via the local study contact (e.g. Site Monitor).

Refer to the Module on Clinical Trial Supplies in the SPM for details and instructions on the temperature excursion reporting and usage decision process, packaging and accountability of the study vaccine(s).

**7.4.2. Replacement of unusable vaccine(s) doses**

In addition to the vaccine doses provided for the planned number of subjects (including over-randomisation when applicable), at least 10% additional vaccine doses will be supplied to replace those that are unusable.

The investigator will use SBIR to obtain the replacement product number. The replacement numbers will be allocated by component. The system will ensure, in a blinded manner, that the replacement product matches the formulation the subject was assigned to by randomisation.

**CONFIDENTIAL**209141 (RSV MAT-011)  
Protocol Amendment 6 Final**7.5. Concomitant medication(s)/product(s) and concomitant vaccinations****7.5.1. Recording of concomitant medications/products and concomitant vaccinations**

At each study visit/contact, the investigator or delegate should question the subject about any medications/products taken and vaccinations received by the subject.

The following concomitant medication(s)/product(s)/vaccine(s) must be recorded in the eCRF.

- All concomitant medications/products, except vitamins and dietary supplements, administered during the period of 31 days post primary vaccination and 2nd vaccination.
- Any concomitant vaccination administered in the period starting 30 days before the dose of study vaccine(s) and ending at the last study visit/contact (Day -30 to Day 181 post 2nd vaccination).
- Prophylactic medication (i.e. medication administered in the absence of ANY symptom and in anticipation of a reaction to the vaccination).

An anti-pyretic is considered to be prophylactic when it is given in the absence of fever and any other symptom, to prevent fever from occurring fever is defined as temperature. 38.0°C/100.4°F regardless the location of measurement. The preferred location for measuring temperature in this study will be the oral cavity.

- Any concomitant medications/products/vaccines leading to the withdrawal or non-eligibility of the subject from the study.
- Any concomitant medications/products/vaccines relevant to an SAE to be reported as per protocol or administered at any time during the study period for the treatment of an SAE. In addition, concomitant medications relevant to SAEs need to be recorded on the expedited Adverse Event report.
- Any antipyretic administered in the period starting 6 hours before vaccination and ending 12 hours after vaccination needs to be recorded on the specific page of the eCRF.
- The Medical Monitor should be contacted if there are any questions regarding concomitant or prior therapy.

**7.5.2. Concomitant medications/products/vaccines that may lead to the elimination of a subject from per-protocol analyses**

The use of the following concomitant medications/products/vaccines will not require withdrawal of the subject from the study but may determine a subject's evaluability in the per-protocol analysis. See Section 10.2 for populations to be analysed.

**CONFIDENTIAL**209141 (RSV MAT-011)  
Protocol Amendment 6 Final

Any investigational or non-registered product (drug or vaccine) other than the study vaccine(s) used during the study period.

- Immunosuppressants or other immune-modifying drugs administered chronically (i.e. more than 14 days in total) during the study period. For corticosteroids, this will mean prednisone  $\geq 5$  mg/day (for adult subjects) or  $\geq 0.5$  mg/kg/day (for paediatric subjects), or equivalent. Inhaled and topical steroids are allowed.
- Long-acting immune-modifying drugs administered at any time during the study period (e.g. infliximab).
- A vaccine not foreseen by the study protocol administered during the period starting 30 days before the dose and ending 30 days after each dose of vaccine(s).

Note: In case an emergency mass vaccination for an unforeseen public health threat (e.g.: a pandemic) is organised by the public health authorities, outside the routine immunisation program, the time period described above can be reduced if necessary for that vaccine provided it is licensed and used according to its Summary of Product Characteristics (SmPC) or Prescribing Information and according to the local governmental recommendations and provided a written approval of the Sponsor is obtained.

- Immunoglobulins and/or any blood products administered during the study period.
- Drug and/or alcohol abuse.

## **7.6. Intercurrent medical conditions that may lead to elimination of a subject from per-protocol analyses**

At each study visit subsequent to the vaccination visit, it must be verified if the subject has experienced or is experiencing any intercurrent medical condition that may lead to elimination from per protocol analysis. If it is the case, the condition(s) must be recorded in the eCRF.

For example, subjects may be eliminated from the per-protocol set for immunogenicity if, during the study, they incur a condition that has the capability of altering their immune response (i.e. varicella) or are confirmed to have an alteration of their initial immune status.

## **7.7. Contraindications to subsequent vaccine(s) administration**

N/A

## **7.8. Warnings and precautions**

Warnings and precautions to vaccination must be checked at the beginning of each vaccination visit.

Refer to the local approved product Prescribing Information for *Boostrix*.

**CONFIDENTIAL**209141 (RSV MAT-011)  
Protocol Amendment 6 Final

## 7.9. Treatment after completion of the study

The investigator is encouraged to share the immunological assay results for *Boostrix* non-responders with the study subjects.

For the subjects identified as non-responders, it remains the responsibility of the investigator in charge of the subject's clinical management to determine the medical care needed as per local/regional practices (such as re-vaccination of the subject(s)).

## 8. STUDY ASSESSMENTS AND PROCEDURES

Study procedures and their timing are described in the SoA (Section 2).

Protocol waivers or exemptions are not allowed unless necessary for the management of immediate safety concerns.

Immediate safety concerns should be discussed with the sponsor immediately upon occurrence or awareness to determine if the subject(s) should discontinue study treatment.

Adherence to the study design requirements, including those specified in the SoA, is essential and required for study conduct.

- All screening evaluations must be completed and reviewed to confirm that potential subjects meet all eligibility criteria. The investigator will maintain a screening log to record details of all subjects screened and to confirm eligibility or record reasons for screening failure, as applicable. The lab results will be considered valid for a period of 30 days from the date of initial screening.

Procedures conducted as part of the subject's routine clinical management (e.g. blood count) and obtained before signing of ICF may be utilised for screening or baseline purposes provided the procedure met the protocol-specified criteria and was performed within the time frame defined in the SoA.

### 8.1. Study Procedures During Special Circumstances

**During special circumstances (e.g., the COVID-19 pandemic), the specific guidance from local public health and other competent authorities regarding the protection of individuals' welfare must be applied.**

For the duration of such special circumstances:

- Reconsent of subjects for the study extension may be placed on hold. Decisions on re-starting will be made in a manner consistent with guidance from public health and other competent authorities.

**CONFIDENTIAL**209141 (RSV MAT-011)  
Protocol Amendment 6 Final

- Informed consent must take place in a face to face contact with the investigator but informing the potential subject ahead of giving written consent may be done remotely for example by mailing the informed consent or telephone or videotelephony conversation.
- Certain procedures may be performed at an alternate location. This includes, signing of informed consent, physical examination and vaccine dosing. If vaccinating in an alternate location, it must be assured that trained staff and equipment are available to manage an acute vaccine reaction. Biological samples may be collected at a different location\* other than the study site or at participant's home. Biological samples should not be collected if they cannot be processed in a timely manner or appropriately stored until the intended use.
- Safety follow-up may be made by a telephone call, other means of virtual contact or home visit, if appropriate.
- "Medically attended visits" include instances where, due to the special circumstances, the subject cannot seek medical advice for symptoms/an illness by visiting a medical facility or arranging for a home visit, and seeks this advice instead via telephone, SMS, email, videotelephony or telemedicine, or other means.
- The paper Diary card provided to the subject may be transmitted from and to the site by electronic means and or conventional mail.
- If despite best efforts it is not possible to collect the biological samples within the interval predefined in the protocol (see [Table 4](#)), then the interval may be extended up to a maximum length described in [Table 10](#), however efforts should be made to adhere as closely as possible to the optimal timing.
- If despite best efforts it is not possible to administer the dose of study vaccine as defined in the protocol (see [Table 4](#)), a maximum dose interval described in [Table 10](#) may be used, however efforts should be made to adhere as closely as possible to the optimal timing.

**Table 10      Intervals between study visits under Special Circumstances**

Interval	Optimal timing	Allowed interval	Adapted interval under special circumstances
Screening Visit → Visit 1	≤7 days	-7- 1 days	-30 to 1 days
Visit 1 → Visit 2	8 days	7- 10 days	7- 10 days
Visit 1 → Visit 3	31 days	30- 45 days	30 – 60 days
Visit 1 → Phone Contact 1	181 days	165- 195 days	165 – 195 days
Visit 4 → Visit 5		-7 to 1 days	-30 – 1 days*
Visit 1 → Visit 5	365 days	365-548 days**	
Visit 5 to Phone Contact 2	8 days	7- 10 days	7- 10 days
Visit 5 → Visit 6	31 days	30- 45 days	30 – 90 days
Visit 5 → Phone Contact 3	181 days	165- 195 days	165 – 195 days

\*From 30 days prior to vaccination up to and including the day of vaccination.

\*\* For a 6-month period ≥12 to <18 months post 1st vaccination

Impact on the per protocol set for immunogenicity will be determined on a case by case basis.

**CONFIDENTIAL**209141 (RSV MAT-011)  
Protocol Amendment 6 Final

- Any impact of above-mentioned measures on the study results will be described in the clinical study report.

\* It is the investigator's responsibility to identify an alternate location. The investigator should ensure that this alternate location meets ICH GCP requirements, such as adequate facilities to perform study procedures, appropriate training of the staff and documented delegation of responsibilities in this location. This alternate location should be covered by proper insurance for the conduct of study on subjects by investigator and staff at a site other than the designated study site.

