### 10.3.3. Immunogenicity analyses

The primary analysis will be based on the Per Protocol set for analysis of immunogenicity. If, in any study group and at any timepoint, the percentage of enrolled or vaccinated subjects with serological results excluded from the Per Protocol set for analysis of immunogenicity is 5% or more, a second analysis based on the Exposed Set will be performed to complement the Per Protocol analysis.

Endpoint	Statistical Analysis Methods
Primary	
(US + ex-US data to be pooled for the first vaccination)
 
For each group, at each time point that blood samples are collected for humoral immune response and for each assay (unless otherwise specified):
 
 
• GMCs/GMTs and their 95% CI will be tabulated and represented graphically pooled.
 
• Geometric mean of ratios of antibody titer/concentrations at each individual post-vaccination time point over pre-vaccination (screening) will be tabulated with 95% CI pooled.
 
• Antibody titer/concentration will be displayed using reverse cumulative curves pooled.
 
• The kinetics of GMT/GMCs will be plotted as a function of time for subjects with results available at all time points pooled.
 
• The GMT/GMCs ratio and their 90% CI between RSVPreF3 dTpa and RSVPreF3 alone in terms of RSV-A Nab titers and RSV IgG antibody concentrations may be calculated at Screening, and/or Day 8, and/or Day 31 pooled for all subjects.
 
• A further exploratory between-groups analysis will be performed at Day 8 or Day 31 using an ANCOVA model by including study groups, study formulation (US and ex-US), age category, and level of antibodies at Screening as covariates.
 

**CONFIDENTIAL**209141 (RSV MAT-011)  
Protocol Amendment 6 Final

Endpoint	Statistical Analysis Methods

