2090.Vx	Subjects did not comply with blood sample schedule: 
 For PPS at Day 8, check the interval from vaccination to day 8 BS = 7 – 10 days; For PPS at Day 31, check the interval from vaccination to day 31 BS = 30 – 45 days; For PPS at Visit 6, check the interval from Visit to Visit 5 BS = 365 – 548 days; 	Visit 2/Day 8 Visit 3/Day 31 Visit 4 Visit 6	Immunogenicity
2100.Vx	Serological results not available post-vaccination	Visit 2/Day 8 Visit 3/Day 31 Visit 4 Visit 6	Immunogenicity
2120.Vx*	Obvious incoherence or abnormality or error in data	Visit 2/Day 8 Visit 3/Day 31 Visit 4 Visit 6	Immunogenicity
2130.Vx	Testing performed on samples not aligned with ICF	Visit 2/Day 8 Visit 3/Day 31 Visit 4 Visit 6	Immunogenicity

*Attribution of these elimination codes to subject need CRDL review of individual listing

** Attribution of code 1070 to a subject requires CRDL confirmation

Vx+ indicates subjects whose immunogenicity data will be eliminated from a specific visit onwards; Vx indicates subjects whose immunogenicity data will be eliminated from a specific visit.

DOB-Date of Birth, VAC-Vaccination, BS- Blood Sample

4.2.3. Elimination from solicited safety set**4.2.3.1. Excluded subjects****4.2.3.1.1. *Solicited safety set***

Code 1030 (Study vaccine not administered at all), code 800 (fraudulent data) and code 900 (invalid informed consent) and code 1160 (no post-vaccination solicited safety data) will be used for identifying subjects eliminated from the solicited safety set.

5. STATISTICAL ANALYSES**5.1. Demography****5.1.1. Analysis of demographics/baseline characteristics planned in the protocol**

These analyses will be performed on the Exposed set and on the Per protocol set for immunogenicity.

For all subjects, demographic characteristics (e.g., age at vaccination (18–32; 33–45 years), race and ethnicity, vaccination history will be summarized by overall and vaccine group using descriptive statistics.

- Frequency tables will be generated for categorical variables such as age
- Mean, standard deviation, median, minimum and maximum will be provided for continuous data such as age, height, weight and body mass index (BMI).

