7. CONDUCT OF ANALYSES

7.1. Sequence of analyses

7.1.1. First and final study

Analyses to evaluate objectives and endpoints will be performed in steps.

- A **first analysis** will be performed on all data available and as clean as possible, when data for at least primary and secondary endpoints pertaining to safety and immunogenicity up to Day 31 are available. At this point, the statistician will be unblinded (i.e. individual subject treatment assignments will be available), but no individual listings will be provided to the study team. Given that summary safety results may unblind some specific subjects, the study will be considered as single-blind from this point onwards, subjects and investigators will be unblinded after Day 181 post 1st vaccination. The investigators will be provided with the individual data listings or with the randomization listings after Day 181.
- The **second analysis** will evaluate safety data and will be performed when **all subjects** have completed visits up to (and including) C1 (Day 181) and the data are available. From this point the study is unblinded and will continue as an open label study.
- The **third analysis** will evaluate safety and immunogenicity data and will be performed when **all subjects** have completed visits up to (and including) Visit 6 (Day 31 post 2nd dose vaccination) and the data are available. At this time, any available safety data will also be provided.
- The final end-of-study will be performed when all data for at least primary and secondary endpoints up to study conclusion at Day 181 post 2nd dose vaccination (C3) are available. An integrated clinical study report containing all available data will be written and made available to the investigators

The final study report will contain at least the final analyses of all primary and secondary endpoints. these analyses will be documented in an amended study report. If the data for tertiary endpoints become available at a later stage, (an) additional analysis/ analyses will be performed.

Description	Disclosure Purpose (CTRS=public posting, SR=study report, internal)
First Analysis (E1_02)	Internal, Public disclosure
Second Analysis (E1_03)	Internal
Third Analysis (E1_04)	Internal
Final Analysis (E1_01)	Public disclosure, Study report

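### Per-protocol status of samples taken in the widened pandemic windows is left to undefined case-by-case judgement, which conflicts with the SAP at Day 31 and is unconstrained at Visit 6

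*Protocol*

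**What the plan says.** Protocol 8.1, Table 10, sets adapted intervals for special circumstances. Visit 1 to Visit 3 goes from 30-45 to 30-60 days, Visit 5 to Visit 6 from 30-45 to 30-90 days, and Visit 4 may fall up to 30 rather than 7 days before the second dose. The consequence for the analysis set is one sentence: "Impact on the per protocol set for immunogenicity will be determined on a case by case basis". Any impact of these measures is to be described in the study report.

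The set concerned is the main one for immunogenicity. Protocol 10.3.3: "The primary analysis will be based on the Per Protocol set for analysis of immunogenicity". If 5% or more of subjects with serology are excluded in any group at any timepoint, "a second analysis based on the Exposed Set will be performed to complement the Per Protocol analysis".

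SAP 4.2.2.1, Table 4, handles timing through code 2090.Vx:

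- Day 31: "For PPS at Day 31, check the interval from vaccination to day 31 BS = 30 – 45 days".
- Visit 6: "For PPS at Visit 6, check the interval from Visit to Visit 5 BS = 365 – 548 days".
- Visit 4: listed as a timepoint for the code, with no interval given.

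Codes marked with an asterisk carry the note "Attribution of these elimination codes to subject need CRDL review of individual listing". Code 2090.Vx has no asterisk. The SAP contains no special-circumstances rule.

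On blinding, Protocol 7.3 says that after the Day 181 contact the investigator and subject learn the assignment, and "The study extension will then be conducted as an open label study". SAP 7.1.1 says of the time after the second analysis: "From this point the study is unblinded and will continue as an open label study".

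**The concern.** A late sample generally has a lower titre than one taken on schedule, so keeping or dropping it moves the group GMT. A rule on late samples should therefore be fixed before anyone sees the result. Here one document leaves the decision open and the other either fixes it differently (Day 31) or does not address it (Visit 6). Neither document requires the decision to be made without knowledge of group or before the serology is released.

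At stake are the definition of the Day 31 per-protocol set, on which the RSV-A non-inferiority criterion in SAP 5.2.2.1 is read, and the credibility of the Visit 6 GMTs and Visit 6 over Visit 4 ratios, which are summarised by first-dose level.

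**Working it through.** **Step 1: the documents side by side.**

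| Sample | Protocol Table 4 | Protocol Table 10 | SAP code 2090.Vx | Result |
|---|---|---|---|---|
| Visit 3 | 30-45 days | 30-60 days, case by case | 30-45 days, no review | Conflict for days 46-60 |
| Visit 6 | 30-45 days after Visit 5 | 30-90 days, case by case | 365-548 days, referring to Visit 5 | No SAP sampling window; days 46-90 open |
| Visit 4 | Day -7 to day of dose 2 | Day -30 to day of dose 2, case by case | None | Open |

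In Protocol Table 4, 365-548 days is the Visit 1 to Visit 5 interval, the time between doses. The Schedule of Activities plans no immunogenicity sample at Visit 5. The SAP's Visit 6 line therefore checks dose timing, not sample timing.

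The SAP is not simply older. Table 10 came in with Protocol Amendment 4 (28 August 2020), the current SAP is dated 3 December 2020, and Protocol Amendment 6 (9 April 2021) keeps the sentence.

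**Step 2: nearest design figure.** The point does not rest on any figure in the plan. As a check, Protocol Table 19 gives 92.7% power for 100 per group, GMT ratio 1.0, SD 0.4, margin 0.176 on the log10 scale and one-sided 5%. Recomputation gives 92.9% (normal) and 92.7% (noncentral t).

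**Step 3: effect of keeping late samples.** Assume log-linear decline with half-life h, and late samples otherwise like the rest. Relative to Day 31, a sample at day d has titre r = 0.5^((d-31)/h). If a share s of samples is late, the group GMT is multiplied by r^s compared with dropping them.

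| h (days, assumed) | r at Day 60 | r at Day 90 | GMT factor, 10% at Day 90 | GMT factor, 20% at Day 90 |
|---|---|---|---|---|
| 60 | 0.72 | 0.51 | 0.93 | 0.87 |
| 90 | 0.80 | 0.63 | 0.96 | 0.91 |
| 120 | 0.85 | 0.71 | 0.97 | 0.93 |
| 180 | 0.89 | 0.80 | 0.98 | 0.96 |

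The range is 0.87 to 0.98, a fall of about 2-13%. For Visit 3 with the same shares at Day 60, it is 0.72^0.2 = 0.94 to 0.89^0.1 = 0.99, a fall of about 1-6%. These are shifts in one group's GMT. If lateness and decisions were balanced across groups, the between-group ratio would largely cancel them.

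**Step 4: what the 5% trigger leaves open.** Below 5%, at most 2 of 50 or 4 of 100 can be excluded. As an outer bound, suppose those were the highest titres, with normal log10 titres. By simulation the group GMT is then multiplied by about 0.94 at SD 0.3, 0.92 at SD 0.4 and 0.90-0.91 at SD 0.5. In the other direction, keeping late samples excludes nobody, so it never adds to the trigger.

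**The case against.** The strongest reply is that two separate problems should not be run together. The conflict between a fixed and a flexible rule is at Day 31, in the observer-blind part. Open-label knowledge arises in the extension, where the SAP has no fixed Visit 6 window to conflict with. This is correct and limits the point.

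A reader might infer more: that treatment-aware staff can shape the set used for the primary endpoints. The documents do not support that, for four reasons.

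- Primary immunogenicity endpoints stop at Day 31. Visit 4 and Visit 6 immunogenicity is secondary.
- Primary safety, including after the second dose, uses the Exposed Set.
- Every woman receives the same 120 µg second dose, so awareness means awareness of the first-dose group.
- No section says who decides, or that titres are available to them. The laboratory is blinded. What can be said is that nothing rules such knowledge out.

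It is also fair that the half-life and share in Step 3 are assumed, that placing every late sample at Day 90 is the extreme, and that dropping 10-20% would trigger the Exposed Set analysis, so both results would appear. That safeguard works against heavy exclusion. It does not work against selective exclusion below 5%, or against discretionary retention.

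Finally, the Day 31 conflict may concern no sample. Table 10 dates from August 2020, and the rationale for the April 2020 amendment already contrasts the existing cohort with women still to be enrolled. Enrolment dates are not given, so this remains an inference.

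**Conclusion.** The point stands in limited form. The protocol's rule for Table 10 samples is discretionary and unspecified. It contradicts the SAP for Visit 3 samples on days 46-60. At Visit 6 and Visit 4 no SAP sampling window constrains it, and the Visit 6 line cites the wrong interval. In the extension the discretion can be exercised knowing the first-dose group, which is the grouping by which results are summarised; this touches secondary immunogenicity endpoints only.

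The size is conditional: about 2-13% on a Visit 6 GMT if 10-20% of samples were at Day 90 and the half-life were 60-180 days. Neither input comes from the documents, and they do not show that any sample was taken in a widened window. This is an avoidable opening for bias and an inconsistency to remove, not evidence that any result is biased.

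**What to change.** 1. In Protocol 8.1, replace the case-by-case sentence with a reference to SAP code 2090.Vx. The visit scheduling in Table 10 is untouched; only analysis-set membership is fixed.
2. In SAP 4.2.2.1, make the Visit 6 check under code 2090.Vx the Visit 5 to Visit 6 sampling interval in Protocol Table 4 (30-45 days). Add the Protocol Table 4 interval for Visit 4 (from 7 days before the second dose up to and including that day).
3. State that a sample outside its window leaves the per-protocol set at that visit only and stays in the Exposed Set analysis. Report that analysis whenever any Table 10 sample is excluded, whether or not 5% is reached.
4. State that timing-based exclusions are made without knowledge of group and are final before that visit's serology is released. Codes that depend on the results themselves (2100, results not available; 2120, incoherent or abnormal data) are exempt from the pre-release rule.

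The cost is wording and a somewhat smaller per-protocol set. At Day 31, on Table 19's assumptions (ratio 1.0, SD 0.4, one-sided 5%), power by the t calculation goes from 92.7% with 100 per group to 91.6% with 95 and 90.2% with 90.
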